10.2 LABORATORY EVALUATIONS

The actual values and absolute changes from Part A period baseline and Part B baseline for the continuous laboratory parameters will be summarized in SI units by treatment at each scheduled visit for Part A and Part B respectively.

The number and percentage of subjects with at least 1 laboratory abnormality meeting the threshold analysis criteria during the Treatment Emergent Period for Part A and Part B will be summarized by treatment. The Thresholds Range Analyses criteria are provided in [Appendix III](#).

Results of urinalysis and serum/urine pregnancy tests will be listed in individual subject data listings only. In addition, a listing containing individual subject laboratory measurements outside the reference ranges will be provided. This listing will include data from scheduled and unscheduled time points.

Urine sodium, potassium and urine sodium to potassium ratios will be summarized by treatment.

1006696
Parion Sciences Incorporated
CLEAN-PCD
SAP Version 1.0

Serum potassium exceeding 1.1 * upper limit of normal (ULN) and/or plasma potassium exceeding 1.1 * ULN will also be summarized and listed.

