### 11.6.2 Clinical Laboratory Assessments

Blood and urine samples will be analyzed at a central laboratory with the exception of urine pregnancy tests, which will be analyzed locally. At the Screening Visit, blood specimens will be collected for safety laboratory tests. On Day 1, Day 57, and Day 85, blood samples will be collected before the first dose of the study drug in the corresponding Treatment Period.

Blood and urine samples for clinical laboratory assessments will be collected as shown in [Table 3-1](#), [Table 3-2](#), and [Table 3-3](#). Laboratory test results that are abnormal and considered clinically significant will be reported as AEs (see [Section 13.1](#)).

The laboratory test panels are shown in [Table 11-1](#).

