6.2.2 Treatment Emergent Period

Treatment-emergent (TE) period for Part A Treatment Period 1:

1006696
Parion Sciences Incorporated
CLEAN-PCD
SAP Version 1.0

- The Treatment-Emergent Period will correspond to the interval from the first dose date of Treatment Period 1 to 28 days after the last dose date of Treatment Period 1 or the date before the first dose date of Treatment Period 2 or the safety follow-up visit, whichever occurs earlier.

TE period for Part A Treatment Period 2:

- The treatment emergent period will correspond to the interval from the first dose date of Treatment Period 2 to 28 days after the last dose date of Treatment Period 2 or the date before the first dose date of Part B or the safety follow-up visit, whichever occurs earlier.

Treatment-Emergent Period for Part B:

- The treatment emergent period will correspond to the interval from the first dose date of study drug in Part B to 28 days after the last dose date of Part B or the safety follow-up visit, whichever occurs earlier.

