10.1 ADVERSE EVENTS

[figure not shown]
For analysis purposes, AEs will be classified as pre-treatment adverse events (AEs) or TEAEs, defined as follows:

Pre-treatment AEs are defined as any AEs that started before the initial dosing of study drug.

TEAE: any AE that increased in severity or that was newly developed during the treatment emergent period for Part A Treatment Period 1 or Part A Treatment Period 2 or Part B. An AE that starts (or increases in severity) during a specific Part A Treatment Period or Part B will be attributed to the study drug the subject was receiving during the corresponding Part A Treatment Period or Part B.

1006696
Parion Sciences Incorporated
CLEAN-PCD
SAP Version 1.0

For AEs with missing or partial start date, if there is no clear evidence that the AEs started (or increased in severity) before the first dose of Part A, the start date will be imputed to the first dosing date of Part A and the AE assigned to the treatment in Part A Treatment Period 1. For AEs with missing or partial start date, if there is no clear evidence that the AEs started (or increased in severity) before the first dose of Part B, the start date will be imputed to the first dosing date of Part B and the AE assigned to the treatment in Part B.

For the cases in which the end of treatment emergent Period 2 is on the same day as the start of treatment emergent Period for Part B, any AE starting on the same day as start of treatment emergent Period for Part B, will be assigned to the treatment in Part B.

AE summary tables for Part A and B will be presented for TEAEs only and will include the following:

[figure not shown]
- All TEAEs
- TEAEs by worst/highest relationship (includes Related, Possibly Related, Unlikely Related and Not Related)
- TEAEs by maximum severity (includes Mild, Moderate, Severe, and Life threatening)
- TEAEs leading to treatment discontinuation
- TEAEs leading to drug interruption
- Serious TEAEs
- TEAEs leading to death
- Frequently reported TEAEs

A frequently reported TEAE is defined as more than 2 subjects who have TEAE preferred term incidence for at least 1 treatment group.

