10.7 PULSE OXIMETRY

The summary of actual values and absolute changes from Part A period baseline values and Part B period baseline will be presented by treatment at each scheduled time point for the percent of oxygen saturation by pulse oximetry for Part A and Part B respectively.

The number and percentage of subjects with shift changes from Part A period baseline and Part B baseline (normal/missing and low: Normal oxygen saturation: $>95\%$, low oxygen saturation: $\leq 95\%$) to the lowest percent of oxygen saturation during the Part A and B treatment emergent period will be tabulated by treatment.

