APPENDIX III LIST OF THRESHOLD RANGE ANALYSIS CRITERIA

Threshold Criteria for **Laboratory Tests**

Parameter	Criteria	Comments
Clinical Chemistry		
CPK	>ULN - ≤ 2.5 x ULN >2.5 - ≤ 5 x ULN >5 - ≤ 10x ULN >10 x ULN	CTCAE grades 1-4
Creatinine	>ULN - ≤ 1.5 x ULN >1.5 - ≤ 3.0 x ULN >3.0 - ≤ 6.0 x ULN >6.0 x ULN	CTCAE grades 1-4
Blood Urea Nitrogen	>ULN - ≤ 1.5 x ULN >1.5 - ≤ 3.0 x ULN >3.0 - ≤ 6.0 x ULN >6.0 x ULN	Same criteria as creatinine No CTCAE
Sodium	Hyponatremia <LLN - ≥130 mmol/L <130 - ≥120 mmol/L <120 mmol/L Hypernatremia >ULN - ≤ 150 mmol/L >150 mmol/L - ≤155 mmol/L >155 mmol/L - ≤ 160 mmol/L >160 mmol/L	CTCAE grade 1, 3, 4 (No CTCAE grade 2) CTCAE grade 1-4
Potassium (Plasma)	Hypokalemia <LLN - ≥ 2.5 mmol/L <2.5 - ≥ 2.0 mmol/L <2.0 mmol/L Hyperkalemia >ULN - ≤ 5.1 mmol/L	 CTCAE grade 1-4

[figure not shown]
1006696
 Parion Sciences Incorporated
 CLEAN-PCD
 SAP Version 1.0

	>5.1 – ≤ 5.6 mmol/L >5.6 – ≤ 6.0 mmol/L >6.0 mmol/L	
Potassium (Serum)	Hypokalemia <LLN – ≥ 3.0 mmol/L <3.0 – ≥ 2.5 mmol/L <2.5 mmol/L	CTCAE grade 1&2, 3, 4 (Grade 1 and 2 are the same)
	Hyperkalemia >ULN – ≤ 5.5 mmol/L >5.5 – ≤ 6.0 mmol/L >6.0 – ≤ 7.0 mmol/L >7.0 mmol/L	CTCAE grade 1-4
Glucose	Hypoglycemia <3.0 – ≥ 2.2 mmol/L <2.2 – ≥ 1.7 mmol/L <1.7 mmol/L	CTCAE grade 1-4
	Hyperglycemia >ULN - ≤ 8.9 mmol/L >8.9 – ≤ 13.9 mmol/L >13.9 – ≤ 27.8 mmol/L >27.8 mmol/L	CTCAE grade 1-4
Albumin	<35 - ≥ 30 g/L <30 – ≥ 20 g/L <20 g/L	CTCAE grade 1-3
Amylase	>ULN - ≤ 1.5 x ULN >1.5 – ≤ 2.0 x ULN >2.0 – ≤ 5.0 x ULN >5.0 x ULN	CTCAE grade 1-4
Lipase	>ULN - ≤ 1.5 x ULN >1.5 – ≤ 2.0 x ULN >2.0 – ≤ 5.0 x ULN >5.0 x ULN	CTCAE grade 1-4
Direct bilirubin	>ULN - ≤ 1.5 x ULN >1.5 – ≤ 2 x ULN >2 – ≤ 3 x ULN >3 – ≤ 10 x ULN >10 x ULN	Same Criteria as Total Bilirubin No CTCAE Not in DILI Guidance
GGT	>ULN - ≤ 2.5 x ULN >2.5 – ≤ 5.0 x ULN >5.0 – ≤ 20.0 x ULN >20.0 x ULN	CTCAE grade 1-4
Calcium	Hypercalcemia >ULN - ≤ 2.9 mmol/L >2.9 – ≤ 3.1 mmol/L >3.1 – ≤ 3.4 mmol/L >3.4 mmol/L	CTCAE grade 1-4

1006696
 Parion Sciences Incorporated
 CLEAN-PCD
 SAP Version 1.0

	Hypocalcemia <LLN - ≥ 2.0 mmol/L <2.0 - ≥ 1.75 mmol/L <1.75 - ≥ 1.5 mmol/L <1.5 mmol/L	CTCAE grade 1-4
Magnesium	Hypermagnesemia >ULN - ≤ 1.23 mmol/L >1.23 - ≤ 3.30 mmol/L >3.30 mmol/L	CTCAE grade 1, 3, 4 No CTCAE grade 2
	Hypomagnesemia <LLN - ≥ 0.5 mmol/L <0.5 - ≥ 0.4 mmol/L <0.4 - ≥ 0.3 mmol/L <0.3 mmol/L	CTCAE grade 1-4
ALT	>ULN - ≤ 3 xULN >3 - ≤ 5 xULN >5 - ≤ 8 xULN >8 - ≤ 20.0 xULN >20.0 x ULN	Per FDA DILI Guidance Jul 2009 and CTCAE

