	Tachycardia	Per HV grade 1, 2, 3, plus shift change
	>100 bpm >115 bpm >130 bpm Increase from baseline ≥ 10 bpm Increase from baseline ≥ 20 bpm >100 bpm and increase from baseline ≥ 10 bpm >100 bpm and increase from baseline ≥ 20 bpm	
PR	≥ 240 ms	
	≥ 300 ms ≥ 200 ms and increase from baseline ≥ 40 ms ≥ 200 ms and increase from baseline ≥ 100 ms	
QRS	>110 ms	
	>160 ms Increase from baseline ≥ 20 ms Increase from baseline ≥ 40 ms	
QTcF	>450 ms (Male)	
	>470 ms (Female) ≥ 500 ms Increase from baseline >10 ms Increase from baseline >20 ms Increase from baseline >40 ms Increase from baseline >60 ms	

Threshold Criteria for Vital Signs

Parameter	Threshold Criteria	Comments
HR	Same PCS as above in ECG category	

1006696
Parion Sciences Incorporated
CLEAN-PCD
SAP Version 1.0

SBP	SBP increased	809/770 analyses
	>140 mmHg >160 mmHg >10 mmHg increase from baseline >20 mmHg increase from baseline	
	>140 mmHg & >10 mmHg increase from baseline >140 mmHg & >20 mmHg increase from baseline >160 mmHg & >10 mmHg increase from baseline >160 mmHg & >20 mmHg increase from baseline	
	SBP decrease	Per HV grade 1, 3, plus shift change
	<90 mmHg <80 mmHg >10 mmHg decrease from baseline >20 mmHg decrease from baseline	
	<90 mmHg and >10 mmHg decrease from baseline <90 mmHg and >20 mmHg decrease from baseline <80 mmHg and >10 mmHg decrease from baseline <80 mmHg and >20 mmHg decrease from baseline	
DBP	DBP increased	809/770 analyses
	>90 mmHg >100 mmHg >5 mmHg increase from baseline >10 mmHg increase from baseline	
	>90 mmHg and >5 mmHg increase from baseline >90 mmHg and >10 mmHg increase from baseline >100 mmHg and >5 mmHg increase from baseline >100 mmHg and >10 mmHg increase from baseline	

1006696
Parion Sciences Incorporated
CLEAN-PCD
SAP Version 1.0

	DBP decreased	
	<60 mmHg	
	<45 mmHg	
	>5 mmHg decrease from baseline	
	>10 mmHg decrease from baseline	
	<60 mmHg and >5 mmHg decrease from baseline	
	<60 mmHg and >10 mmHg decrease from baseline	
	<45 mmHg and >5 mmHg decrease from baseline	
	<45 mmHg and >10 mmHg decrease from baseline	
Weight	Weight gain	CTCAE grade 1-3
	≥5 % increase from baseline	
	≥10 % increase from baseline	
	≥20% increase from baseline	
	Weight loss	CTCAE grade 1-3
	≥5 % decrease from baseline	
	≥10 % decrease from baseline	
	≥20% decrease from baseline	

1006696
 Parion Sciences Incorporated
 CLEAN-PCD
 SAP Version 1.0

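### Laboratory threshold counts require no worsening from baseline, and a window defined by dose date misplaces the Day 1, Day 57 and Day 85 pre-dose samples

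*SAP*

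**What the plan says.** SAP 10.2 plans "The number and percentage of subjects with at least 1 laboratory abnormality meeting the threshold analysis criteria during the Treatment Emergent Period", by treatment, using the criteria in Appendix III. The laboratory rows there are multiples of the upper limit, values below the lower limit, or fixed units, for example ">ULN - ≤ 1.5 x ULN" for creatinine. None refers to baseline. The additional potassium summary in 10.2 (above 1.1 × ULN) has no baseline condition either.

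Other safety data in the same SAP are tied to baseline. An adverse event is treatment-emergent only if it is "any AE that increased in severity or that was newly developed during the treatment emergent period" (10.1). The ECG and vital-sign rows of Appendix III include change criteria such as "Increase from baseline >10 ms". Pulse oximetry gets "The number and percentage of subjects with shift changes from Part A period baseline and Part B baseline" (10.7). Table 3 of the SAP lists no shift table for laboratories.

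SAP 6.2.2 defines the Period 1 window as "the interval from the first dose date of Treatment Period 1" onward, and defines Period 2 and Part B in the same way. Period 2 closes at the latest on the day before the first Part B dose date. Protocol 12.3.1 instead opens each interval at the first dose itself. Protocol 11.6.2 states: "On Day 1, Day 57, and Day 85, blood samples will be collected before the first dose of the study drug".

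**The concern.** A count of subjects in an absolute band mixes two things: values that became abnormal on treatment, and values that were abnormal before treatment and stayed so. In a crossover the second kind is not separated by randomisation. The same subject adds one to the numerator of both treatments in the sequence, so the two percentages converge in relative terms and neither can be read as an incidence under treatment. Laboratory values are part of the primary safety endpoint in both parts.

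The window adds a second problem. If it is set by calendar date, the sample that serves as a period's baseline lies inside the period for which it is the baseline. At the Part A/Part B boundary, the sample that shows the effect of 28 days of Period 2 treatment is credited to the ivacaftor period instead.

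**Working it through.** **Which abnormalities can be carried in.** Protocol 9.2, criterion 15, set against Appendix III:

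- ALT/AST: excluded at ≥3 × ULN. The lowest band, up to 3 × ULN, stays open.
- Bilirubin: excluded above 2 × ULN (Gilbert's syndrome excepted). The two lowest bands, up to 1.5 and up to 2 × ULN, stay open.
- Haemoglobin: excluded below 10.0 g/dL, which is 100 g/L. The lowest band, from LLN down to 100 g/L, stays open.
- Potassium: excluded above ULN in plasma or serum, so the hyperkalaemia bands are largely clean at entry.
- CPK, GGT, amylase, lipase, glucose and white cells: no numeric limit, only the investigator's judgement of clinical significance.

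**Size of the dilution.** The documents give no abnormality rates and no figure to reproduce, so every rate below is an assumption. Let b be the prevalence of a persistent pre-dose abnormality in a band, and e the new-onset risk among the rest.

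- As planned: p = b + (1 − b)e
- With a worsening rule: p = (1 − b)e
- Difference between treatments, either way: (1 − b)(e₁ − e₀)

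| Assumed e (active, control) | b | As planned | Ratio | Difference (points) |
|---|---|---|---|---|
| 6%, 2% | 0% | 6.0 vs 2.0 | 3.00 | 4.0 |
| 6%, 2% | 3% | 8.8 vs 4.9 | 1.79 | 3.9 |
| 6%, 2% | 5% | 10.7 vs 6.9 | 1.55 | 3.8 |
| 6%, 2% | 10% | 15.4 vs 11.8 | 1.31 | 3.6 |
| 6%, 2% | 20% | 24.8 vs 21.6 | 1.15 | 3.2 |
| 10%, 3% | 0% | 10.0 vs 3.0 | 3.33 | 7.0 |
| 10%, 3% | 10% | 19.0 vs 12.7 | 1.50 | 6.3 |
| 10%, 3% | 20% | 28.0 vs 22.4 | 1.25 | 5.6 |

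Worked row: 0.10 + 0.90 × 0.06 = 0.154 and 0.10 + 0.90 × 0.02 = 0.118; 0.154/0.118 = 1.31. Under a worsening rule the same row reads 5.4% vs 1.8%, ratio 3.0, difference 3.6 points. The rule therefore restores the ratio and the meaning of each percentage. It does not change the difference when all treated subjects are the denominator. In that row, 0.10/0.154 = 65% of the subjects counted on active treatment were abnormal before dosing.

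**The window, Day 1 and Day 57.** Blood is drawn before the dose, at the visit where the dose is given. By date, the sample is on the first day of the window. A period has one scheduled post-dose chemistry sample, or two if the mid-period visit is held. Assume, for scale only, a 2.5% chance of an isolated high value per sample, independent between samples. Adding the pre-dose sample then raises the per-analyte rate:

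- one post-dose sample: 2.5% to 1 − 0.975² = 4.9%
- two post-dose samples: 4.9% to 1 − 0.975³ = 7.3%

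**The window, Day 85.** For a subject entering Part B, Day 85 is the first Part B dose date.

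- SAP 6.2.2 ends Period 2 on Day 84, so the Day 85 pre-dose sample falls in the Part B window.
- SAP Appendix VI assigns the Day 85 visit to Period 2, and footnote a requires its assessments to precede Part B dosing.
- SAP 6.2.1 makes the last value before ivacaftor, and after the last Period 2 dose, the Part B baseline.
- Protocol 12.3.1 keeps Period 2 open until the first Part B dose.

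These cannot all hold. Where Day 71 became a telephone call, the only scheduled laboratory sample left in the Period 2 window under 6.2.2 is the Day 57 pre-dose one. SAP 10.1 has a same-day rule for adverse events at this boundary; laboratories have none.

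**The case against.** The strongest reply has four parts.

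First, Appendix VI starts its post-dose windows after Day 1 of each period and sends unflagged records to listings only. If it governs, the pre-dose samples drop out and Day 85 belongs to Period 2. This could be so, but 10.2 defines the count by the treatment-emergent period and does not cite Appendix VI. Appendix VI also keeps a single record per visit, which suits by-visit summaries better than an at-least-one count. Even if it governs, it does not supply a worsening rule.

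Second, absolute bands follow CTCAE or liver-injury guidance for most analytes and look deliberate, and the ECG and vital-sign tables also contain absolute-only rows. That is fair, and it is a reason to keep the absolute table as a supplement. But those tables offer change-based rows beside the absolute ones.

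Third, baseline-relative information exists: changes from period and Part B baseline by visit, a listing of out-of-range values, and clinically significant worsening recorded as adverse events (Protocol 13.1.1.2). This softens the problem, but none of it gives the proportion of subjects who moved to a worse band, by treatment.

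Fourth, the plan reports counts and percentages, not ratios, and the risk difference is little affected. This stands.

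A reader might infer more than the documents support:

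- **That the hyperkalaemia signal is compromised.** Potassium above ULN is excluded at screening, the criteria must still be met at Day 1 (Protocol 8.1.3.1.1), and Protocol 11.6.2.1 acts on hyperkalaemia during the study.
- **That every subject admitted with a mild abnormality counts twice.** That needs persistence or recurrence, and dosing in both periods. An isolated Day 1 value counts at most under the Period 1 treatment.
- **That the SAP calls these abnormalities treatment-emergent.** It says only that they occur during the period.

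**Conclusion.** The point holds in a limited form. Followed as written, SAP 10.2 counts persistent pre-existing abnormalities under each treatment received, mainly in the mild ALT/AST, bilirubin and haemoglobin bands and in analytes without a numeric entry limit. For any b above zero the incidence ratio moves towards 1 and the difference shrinks by the factor (1 − b). Under the assumed 6% and 2%, b of 3% to 20% takes the ratio from 3.0 to between 1.79 and 1.15, and the difference from 4.0 to between 3.9 and 3.2 points. The direction follows from the rule. The sizes rest on assumed rates, on persistence, and on no further worsening among those already abnormal. The higher liver bands and haemoglobin below 100 g/L are little affected.

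The window defect is a conflict between texts: SAP 6.2.2 against Appendix VI footnote a and Protocol 12.3.1. Its most concrete consequence is that, for subjects entering Part B, the end-of-treatment sample of a randomised period can be counted under Part B. This should be corrected before database lock; it does not invalidate the safety analysis.

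**What to change.** 1. In SAP 6.2.2, define the treatment-emergent period for laboratory data by dose date and time. Day 1 and Day 57 pre-dose samples are then baseline only. The Day 85 pre-dose sample belongs to Period 2 and serves as the Part B baseline.
2. In SAP 10.2, count a subject in a band only if the worst post-dose value in the period is in a worse band than the period baseline (Part B baseline in Part B). Keep the absolute-band table as a supplement if wanted.
3. State in 10.2 whether the Appendix VI windows apply to the threshold counts.
4. Optionally, add baseline-to-worst shift tables for potassium, creatinine, ALT/AST, bilirubin and haemoglobin.

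The cost is SAP wording and modest programming, with no new data. Reported incidences become smaller, which a table footnote should explain.

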10.3 VITAL SIGNS

The actual values and absolute changes from Part A period baseline and Part B baseline for the following vital signs measurements will be presented by treatment at each scheduled visit for Part A and Part B respectively: systolic and diastolic blood pressure (mm Hg), body temperature, pulse rate (beats per minute), respiratory rate (breaths per minute), weight (kg), height (cm) and BMI (kg/m²). The number and percentage of subjects with at least 1 threshold analysis event during the treatment emergent period will also be tabulated.

The Thresholds Range Analyses criteria are provided in [Appendix III](#).

10.4 ELETROCARDIOGRAM

A summary of actual values and absolute changes from Part A period baseline and Part B baseline will be provided by treatment at each scheduled visit for Part A and Part B respectively for the following electrocardiogram (ECG) measurements: ventricular heart rate, QRS duration, PR duration, QT duration, RR interval, QTcF. In addition, the number and percentage of subjects with at least 1 threshold analysis event during the treatment emergent period will also be tabulated.

The Thresholds Range Analyses criteria are provided in [Appendix III](#).

10.5 PHYSICAL EXAMINATION

For Part A and Part B, abnormal physical examination results will be presented in individual subject data listings only.

[figure not shown]
10.6 SPIROMETRY

Spirometry data in Part A and Part B will be summarized based on the Part A Safety Set and Part B Safety Set respectively. This will include the number and percentage of subjects at each scheduled time point relative to Part A period baseline value and Part B Baseline value for the following:

- Subjects with ≥ 10 percentage point decrease in ppFEV1
- Subjects with ≥ 15 percentage point decrease in ppFEV1
- Subjects with ≥ 20 percentage point decrease in ppFEV1

1006696
 Parion Sciences Incorporated
 CLEAN-PCD
 SAP Version 1.0

- Subjects with ≥ 0.2 L decrease in FEV1

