#### **12.3.4.6 Spirometry**

##### **Part A**

Spirometry data in Part A will be summarized based on the Part A Safety Set. This will include the number and percentage of subjects at each scheduled time point with predefined decreases in ppFEV1/FEV1 relative to Part A period baseline value.

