APPENDIX VI VISIT WINDOWS

The unscheduled or early withdrawal visit will be mapped to a scheduled visit for analysis using the date of collection/assessment as a basis to determine study day and then study day will be mapped to the intended visit. Table 8 and Table 9 below contain the analysis visit windows.

Table 8. Study windows

Study Period	Scheduled Visit/Day	Study Day Window	Analysis Visit
Period 1	Day 15 Visit	Day >1 - ≤ 22	Day 15
	Day 29 Visit	Day >22 - ≤ 36	Day 29
Period 2	Day 71 Visit	Period 2, Day >1 - ≤ 22	Day 15
	Day 85 Visit	Period 2, Day >22 - ≤ 36 ^a	Day 29
Period 3	Day 99 Visit	Period 3, Day >1 - ≤ 22	Day 15
	Day 113 Visit	Period 3, Day >22 - ≤ 36	Day 29

a: all assessments should happen before Part B dosing time.

For SGRQ, QOL-PCD [REDACTED] hematology, height and weight, [REDACTED] the following windows will be used:

Table 9. Study windows for Day 1 and Day 29 only

Study Period	Scheduled Visit/Day	Study Day Window	Analysis Visit
Period 1	Day 29 Visit	Day >1 - ≤ 36	Day 29
Period 2	Day 85 Visit	Period 2, Day >1 - ≤ 36 ^a	Day 29
Period 3 ^b	Day 113 Visit	Period 3, Day >1	Day 29

a: all assessments should happen before Part B dosing time.

[figure not shown]
b: visit windows for height and weight will only be applied for Period 1 and 2. Height and weight visit windows for Period 3 will be the same as table 6.

Once analysis visit windows are assigned, all visits, including scheduled visits, unscheduled visits, and early termination visits will be eligible for being flagged as the “analyzed record” within the analysis visit window. Note that the scheduled visit should match with the visit for which the visit window is defined. For example: If Day 29 visit falls in the visit window for Day 15, then Day 15 will be assigned to this visit. If no numerical measurement is available within a visit window, the measurement will be considered missing for the visit.

A subject’s individual analysis visit window could potentially contain more than one visit. In the event of multiple visits falling within an analysis visit window or in case of a

1006696
Parion Sciences Incorporated
CLEAN-PCD
SAP Version 1.0

Statistical Analysis Plan

tie, the following rules will be used in sequence to determine the “analyzed record” for the analysis visit window:

- the data closest to the scheduled day will be used.
- If there are multiple measurements with the same distance from the target day, the latest measurement will be used.

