The data not flagged as the “analyzed record” will only be listed in subject listings.

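### The spirometry safety table has no count of subjects with any ppFEV1 or FEV1 fall in the treatment-emergent period, so a fall at an unscheduled or early-termination visit can be missing from it

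*SAP*

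**What the plan says.** SAP 10.6 summarises spirometry for safety as "the number and percentage of subjects at each scheduled time point relative to Part A period baseline value and Part B Baseline value". The four cut-offs are falls of at least 10, 15 and 20 percentage points in ppFEV1 and of at least 0.2 L in FEV1. Protocol 12.3.4.6 has the same unit of counting: "the number and percentage of subjects at each scheduled time point with predefined decreases in" ppFEV1 or FEV1. SAP Table 3 (section 10.8) lists only the frequency of these categories for spirometry, and Appendix III has threshold criteria for laboratory tests, ECG and vital signs but none for spirometry.

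The other measured safety domains look across visits. SAP 10.2 counts subjects "with at least 1 laboratory abnormality meeting the threshold analysis criteria during the Treatment Emergent Period for Part A and Part B". SAP 10.4 says that subjects with "at least 1 threshold analysis event during the treatment emergent period will also be tabulated", and SAP 10.3 does the same for vital signs. SAP 10.7 tabulates the oximetry shift "to the lowest percent of oxygen saturation during the Part A and B treatment emergent period will be tabulated by treatment".

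Appendix VI maps unscheduled and early-withdrawal visits to an analysis visit by study day. When several records share a window, "the data closest to the scheduled day will be used", with ties going to the latest. Records not selected "will only be listed in subject listings". Table 8 has two windows per period, Days 2 to 22 and Days 23 to 36. SAP 6.2.2 sets the Period 1 treatment-emergent period "from the first dose date of Treatment Period 1 to 28 days after the last dose date of Treatment Period 1", or to the day before Period 2 dosing or the safety follow-up if either comes earlier.

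**The concern.** Spirometry is named in the primary safety endpoint of both parts (SAP 4.1.1 and 4.2.1), and the study drug is inhaled. Protocol 8.1.6 provides for unscheduled visits for extra safety assessments and changes in clinical status, and the early-termination visit includes spirometry.

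The selection rule picks the record nearest the target day, not the worst one. A fall recorded at such a visit is tabulated only if it is the sole record in its window or the nearest to target. The rule has no domain limit. What is particular to spirometry is that no summary across visits is specified.

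Per-visit rows also cannot be added up to give subject incidence. A subject with falls at both Day 15 and Day 29 appears in two rows, so even with scheduled visits alone the table does not say how many subjects had any fall. At stake is the by-treatment count of subjects with a fall of a given size. The raw values and the efficacy inference are not at stake.

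**Working it through.** The plan gives no figure on this point to reproduce. The check applies the Appendix VI rules to Period 1.

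**Inputs.** Windows come from Table 8: Days 2 to 22 (21 days, target Day 15) and Days 23 to 36 (14 days, target Day 29), 35 days in all. With last dose on Day 28, the treatment-emergent period ends on Day 28 + 28 = Day 56. That leaves Days 2 to 56 = 55 days after Day 1, of which Days 37 to 56 = 20 have no window.

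**Single case (assumed values).** Period baseline ppFEV1 is 60, an unscheduled Day 24 value is 38, and the Day 29 value is 59.
- Fall at Day 24: 60 − 38 = 22 points, which meets all three ppFEV1 cut-offs.
- Distance to target: |24 − 29| = 5 days against |29 − 29| = 0 days. The Day 29 record is selected.
- Fall at Day 29: 60 − 59 = 1 point. The subject appears in no ppFEV1 row.

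**Day count.** One unscheduled fall is placed on each possible day other than a planned-visit day, with recovery by the planned visits. A day is counted if its record would be selected, and displaced if a planned visit in the same window is selected instead.

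| Planned spirometry after Day 1 | Days considered | Counted | Displaced | No window |
|---|---|---|---|---|
| None | 55 | 35 | 0 | 20 |
| Day 29 on target (Day 15 by telephone) | 54 | 21 | 13 | 20 |
| Day 29 visit held on Day 26 | 54 | 27 | 7 | 20 |
| Day 29 visit held on Day 32 | 54 | 26 | 8 | 20 |
| Days 15 and 29 on target | 53 | 0 | 33 | 20 |
| Visits held on Days 12 and 26 | 53 | 12 | 21 | 20 |
| Visits held on Days 18 and 32 | 53 | 10 | 23 | 20 |

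As an example of the arithmetic, take the Day 29 visit held on Day 26, 3 days from target. Unscheduled Days 27 to 31 are nearer to target (5 days), and Day 32 ties and wins as the later record, giving 6. Adding the 21 days of the first window gives 27. The displaced days are 23 to 25 and 33 to 36, which is 7.

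**Early-termination visit.** With no earlier clinic visit in the period, it is counted on all of Days 2 to 36. After an on-target Day 15 visit, it is displaced on Days 16 to 22 and counted on Days 23 to 36.

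**Gap after Day 36.** Its length depends on the last dose. A subject who stops on Day 10 has a treatment-emergent period ending by Day 38, which leaves 2 days without a window. The gap does not arise in Period 2 for subjects entering Part B, whose Period 2 ends the day before the first Part B dose.

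**The case against.** The strongest reply is that this is rare and mostly covered elsewhere. Early-termination visits are usually tabulated, because a subject who stops mid-period seldom has a competing visit in the same window. The day counts assume recovery by the planned visit, whereas a persistent fall would show in the Day 29 row. The row with no planned spirometry is not a normal path for someone dosed to Day 28, and the 20 days without a window lie in the off-drug washout. Acute post-inhalation falls are already summarised for the first dose (SAP 8.1), adverse event tables exist, and all values are listed. The SAP follows the protocol, its wording on what the spirometry summary includes is not exhaustive, and the table shells are not available. Read literally, the listing-only rule could also remove unscheduled values from the other domains' counts.

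Most of this stands as a limit on frequency. It does not supply the missing count. The adverse event route is not a full substitute either: Protocol 13.1.1.2 does not name spirometry among the assessments whose worsening is recorded as an event, although its list is not closed. The last point is a reason to clarify Appendix VI for all safety domains. One further caution is fair: a count over all assessments depends on how often subjects are measured, which is why the per-visit rows should stay beside it.

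**Conclusion.** The concern holds. As written, the plan can leave a subject with a fall of 20 points or more out of every by-treatment ppFEV1 row, and it gives no incidence of any fall by treatment. In the Period 1 scenarios with at least one planned visit, between 0 of 53 and 27 of 54 possible days would lead to a transient fall being counted. These are day counts under stated scenarios; how many subjects would be affected cannot be estimated from the documents.

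The conclusion rests on three assumptions. Table 8 governs spirometry, which has Day 15, 71 and 99 clinic visits and is not in the visible part of the Table 9 list. The unseen table shells add no count over the whole period. Last dose is on Day 28 for the gap of 20 days. This is a gap in safety reporting that should be closed, with no bearing on the efficacy analysis.

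**What to change.** In SAP 10.6, add by treatment the number and percentage of subjects with at least one fall meeting each of the four existing cut-offs from period baseline (Part A) or Part B baseline. Use as denominator the Safety Set subjects treated in that period. Count any post-baseline assessment in the treatment-emergent period, whether scheduled, unscheduled or early termination. Keep the per-visit rows.

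Two definitions are needed:
- Pre-dose Day 85 records should count in Period 2, in line with footnote a to Table 8. The date-based end of Period 2 in SAP 6.2.2 would otherwise drop them for subjects entering Part B.
- The text should say whether the first-dose post-dose records, already summarised under SAP 8.1, enter this count or have their own line.

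In Appendix VI, state that the rule selecting one record per window does not apply to treatment-emergent threshold and worst-value summaries in any safety domain.

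The cost is one table block from data already collected, these two definitions and one sentence in Appendix VI. Data collection does not change.
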